# **8.1.2** Dinutuximab (Chimeric Monoclonal Antibody 14.18 (UTC)), NSC 764038

**Other Names:** Chimeric Monoclonal Antibody 14.18 (UTC); human/murine anti-GD2 monoclonal antibody; chimeric anti-GD2; chimeric mAb 14.18; ch14.18

Classification: Chimeric/human monoclonal antibody

**Description:** Dinutuximab, Chimeric MOAB 14.18 (UTC) is an anti- $G_{D2}$  monoclonal antibody composed of the variable region heavy and light chain genes of the murine mAb 14. $G_{2a}$  and the human constant region genes for heavy chain  $IgG_1$  and light chain kappa.

Mode of Action: Dinutuximab exerts its antitumor effect by binding specifically to the disialoganglioside  $G_{D2}$ , an antigen found in human tumors of neuroectodermal origin such as melanoma and neuroblastoma. This chimeric antibody has been shown to lyse melanoma and neuroblastoma cells through the process of antibody-dependent cell-mediated cytotoxicity and complement-dependent cytotoxicity. By targeting the  $G_{D2}$  antigen on the cell surface, chimeric MOAB 14.18 may also prevent attachment of circulating malignant cells to the extracellular matrix. Additionally, dinutuximab mediates lysis of several melanoma and neuroblastoma cells lines in a dose dependent manner in the presence of potent mediators of chimeric MOAB 14.18-dependent cytotoxicity, such as human peripheral blood mononuclear cells and granulocytes, in particular neutrophils, especially in the presence of recombinant human granulocyte-macrophage colony-stimulating factor.

**How Supplied:** Dinutuximab is manufactured by United Therapeutics and distributed by the CTEP, DCTD, NCI. **Do not use commercial supply.** Dinutuximab is provided as a sterile solution in single-dose vials containing 17.5 mg/5 mL (3.5 mg/mL) in 20 mM Histidine, 150 mM NaCl, 0.05% Tween 20 at pH 6.8.

**Dose:** 17.5 mg/m^2/dose

**Preparation:** Withdraw the required dose of chimeric dinutuximab from the vial(s) and inject the exact volume for the 17.5 mg/m²/day dose into a 100 mL bag of 0.9% sodium chloride. The use of a filter during preparation is not required.

Route of Administration: Intravenous (IV) infusion.

Method of Administration: The dose will be administered by IV infusion over 10-20 hours per Figure 2.

Storage and Handling: Intact vials should be stored in the refrigerator (2°C to 8°C).

**Stability:** Stability studies of the intact vials are ongoing. Dinutuximab is stable at room temperature for at least 24 hours when diluted to a concentration between 0.044 mg/mL and 0.56 mg/mL; however, the final dosage form should be prepared immediately prior to administration as there is a maximum infusion time of 20 hours. The minimum infusion time for the antibody infusion is 10 hours.

If a storage temperature excursion is identified, promptly return ch14.18 (dinutuximab) to the refrigerator temperature and quarantine the supplies. Provide a detailed report of the excursion (including documentation of temperature monitoring and duration of the excursion) to [contact] for determination of suitability.

# **8.1.3** Agent Ordering and Agent Accountability

NCI-supplied agents may be requested by eligible participating Investigators (or their authorized designee) at each participating institution. The CTEP-assigned protocol number must be used for ordering all CTEP-supplied investigational agents. The eligible participating investigators at each participating institution must be registered with CTEP, DCTD through an annual submission of FDA Form 1572 (Statement of Investigator), NCI Biosketch, Agent Shipment Form, and Financial Disclosure Form (FDF). If there are several participating investigators at one institution, CTEP-supplied investigational agents for the study should be ordered under the name of one lead participating investigator at that institution.

Confirmation of patient enrollment is required for starter supply.

Submit agent requests through the PMB Online Agent Order Processing (OAOP) application. Access to OAOP requires the establishment of a CTEP Identity and Access Management account and the maintenance of an "active" account status, a "current" password, and active person registration status. For questions about drug orders, transfers, returns, or accountability, call or email PMB any time. Refer to the PMB's website for specific policies and guidelines related to agent management.

# 8.1.3.1 Agent Inventory Records

The investigator, or a responsible party designated by the investigator, must maintain a careful record of the receipt, dispensing and final disposition of all agents received from the PMB using the appropriate NCI Investigational Agent (Drug) Accountability Record (DARF) available on the CTEP forms page. Store and maintain separate NCI Investigational Agent Accountability Records for each agent, strength, formulation and ordering investigator on this protocol.

# **8.1.4** Investigator Brochure Availability

The current versions of the IBs for the agents will be accessible to site investigators and research staff through the PMB OAOP application. Access to OAOP requires the establishment of a CTEP IAM account and the maintenance of an "active" account status, a "current" password and active person registration status. Questions about IB access may be directed to the PMB IB Coordinator via email.

### 9 STATISTICAL CONSIDERATIONS

# 9.1 Responsibility for Analyses

The statistical analysis of the data obtained from this trial will be the responsibility of Fred Hutchinson Cancer Center as part of the Pediatric CITN.

# 9.2 Study Design/Endpoints

# **9.2.1** Dose Finding Cohort (Arm A) Primary Endpoint

The primary objective is to determine the safety and tolerability of Hu5F9-G4 (magrolimab) in combination with dinutuximab in children and young adults with relapsed/refractory (R/R) neuroblastoma (NBL) and osteosarcoma, and to determine the recommended phase 2 dose (RP2D) of Hu5F9-G4 (magrolimab) given in combination with dinutuximab. All patients who receive any amount of the study drug will be evaluable for toxicity. There will be two timepoints at which dose limiting toxicities (DLTs) will be measured to establish the maximum tolerated dose (MTD): during the 'single agent Safety Lead-In' in which patients with osteosarcoma or NBL will receive Hu5F9-G4 (magrolimab) during the first 3 weeks, and during Cycle 1 (21 days) of the combination of Hu5F9-G4 (magrolimab) and dinutuximab (Figure 2) as described in Section 6.3. If patients in the 'single agent Safety Lead-in' cohort or during Cycle 1 combination of Hu5F9-G4 (magrolimab) and dinutuximab discontinue participation prior to the safety evaluation for reasons other than the occurrence of a DLT (e.g., withdrawal of consent, rapid tumor progression, death due to rapid tumor progression, AE that does not meet DLT criteria), they will not be evaluable for MTD and will be replaced in the appropriate dose-finding group ('single agent Safety Lead-In' or Cycle 1 of Arm A).

If a patient is replaced to determine safety in Cycle 1 of Arm A, and the dose of Hu5F9-G4 (magrolimab) has NOT been deemed safe, i.e., 3 patients have not completed the Safety Lead-in without DLT, the replaced patient will undergo priming dose of Hu5F9-G4 (magrolimab), undergo the Safety Lead-in and then proceed to Cycle 1. This patient will be evaluable for DLT in the Safety Lead-in group.

If 3 patients have received Hu5F9-G4 (magrolimab) during the Safety Lead-in and the dose of Hu5F9-G4 (magrolimab) has been deemed safe, a patient being replaced in Cycle 1 of Arm A, will undergo a priming dose of Hu5F9-G4 (magrolimab) and proceed directly to Cycle 1 (combination of Hu5F9-G4 (magrolimab) and dinutuximab) for determination of MTD in the combination cohort.

Establishment of safety of the combination of Hu5F9-G4 (magrolimab) and dinutuximab will be completed in the first 3 patients enrolled in Arm B as described in section 6.1.1.2.

The safety and tolerability of Hu5F9-G4 (magrolimab) plus dinutuximab will be assessed by:

- Suspected adverse events, and
- Suspected serious adverse events

#### As evidenced by:

• Changes in clinical laboratory tests (clinical chemistry, hematology, etc).

- Changes in vital signs (blood pressure, pulse, respiratory rate and body temperature).
- Changes in physical exams. Signs and symptoms assessed may require additional testing as clinically indicated such as ECG, PFT, radiographic studies, etc.
- Subject reported signs and symptoms

Safety data will be analyzed per standard methods and interpreted descriptively. Safety data will be summarized for each disease group separately and for both disease groups combined. Adverse events will be assessed using the CTCAE version 5.0 for type and severity of event. Serious Adverse Events will be summarized for each disease group and for both disease groups combined. Reasons for discontinuation of study therapy will be tabulated.

# 9.2.2 Expansion Cohorts B1-3 (Arm B) Primary Endpoint

The primary objective for the expansion cohorts is to Evaluate the Overall Response Rate (ORR) of patients treated with Hu5F9-G4 (magrolimab) at RP2D and dinutuximab (see **Figure 2**) as per **Section** Error! Reference source not found.. The three expansion cohorts are defined as:

Cohort B1: Patients with relapsed/refractory confirmed NBL: measurable NBL/ganglioneuroblastoma;

Cohort B2: Patients with relapsed/refractory evaluable NBL; and

Cohort B3: Patient with relapsed/refractory measurable osteosarcoma.

Each cohort will be evaluated for response which will include a stopping rule for futility as follows:

# Expansion Cohort B1

	Cumulative Number of Responses	Decision
Stage 1: Enter 10 patients	0	Terminate this cohort: agent ineffective
	1 or more	Inconclusive result, continue cohort to enroll to stage 2
Stage 2: Enter additional 10 patients	2 or less	Terminate this cohort: agent ineffective
	3 or more	Terminate this cohort: agent effective

Measurable soft tissue disease will be evaluated as per the International Neuroblastoma Response Criteria (INRC) (Park et al., 2017), and responses will be determined as either complete response (CR), partial response (PR), stable disease (SD) or progressive disease (PD). Response rates will be calculated for the confirmed neuroblastoma cohort whose best response is a CR or PR. Response is defined relative to baseline disease. This combination will not be considered to be of sufficient interest for further evaluation if the true response rate is 5% and of sufficient activity if the true response rate is 25%. If the combination has a true response rate of 5%, the rule described above will identify it of sufficient activity for further study with a probability of 0.07 (type1 error) and the trial will have an expected sample size of 14 with 60% probability of early termination. If the combination has a true response rate of 25%, the rule described above will identify it of sufficient activity for further study with probability 0.88 (power against the alternative hypothesis P = 0.25).

# **Expansion Cohort B2**

Evaluable disease will be evaluated with I-MIBG in conjunction with anatomical imaging or bone marrow aspiration;

FDG-PET may be used for tumors that are not MIBG-avid as per the International Neuroblastoma Response Criteria (INRC). Overall response rate (ORR) as measured by INRC: Initially 10 eligible subjects will be treated with Hu5F9-G4 (magrolimab) and dinutuximab at RP2D (including those in the safety evaluation); if 0 responses occur, enrollment will stop to this cohort. If 1 or more subjects respond, enrollment will continue to a total of 20 subjects with evaluable neuroblastoma treated at the RP2D. If 3 or more evaluable subjects with evaluable disease have a response, this combination in this cohort will be considered of sufficient interest to warrant additional study. The following Simon's optimal two stage design will be used for this cohort:

	Cumulative Number of Responses	Decision
Stage 1: Enter 10 patients	0	Terminate this cohort: agent ineffective
	1 or more	Inconclusive result, continue cohort to enroll to stage 2
Stage 2: Enter additional 10 patients	2 or less	Terminate this cohort: agent ineffective
	3 or more	Terminate this cohort: agent effective

The response criteria for this cohort will be as defined in INRC. Responses will be determined as either complete response (CR), partial response (PR), stable disease (SD), minor response (MR), or progressive disease (PD). Response rates will be calculated for the confirmed neuroblastoma cohort whose best response is a CR or PR. Response is defined relative to baseline disease. This combination will not be considered to be of sufficient interest for further evaluation if the true response rate is 5% and of sufficient activity if the true response rate is 25%. If the combination has a true response rate of 5%, the rule described above will identify it of sufficient activity for further study with a probability of 0.07 (type1 error) and the trial will have an expected sample size of 14 with 60% probability of early termination. If the combination has a true response rate of 25%, the rule described above will identify it of sufficient activity for further study with probability 0.88 (power against the alternative hypothesis P = 0.25).

# **Expansion Cohort B3**

Overall response rate (ORR) as measured by RECIST v1.1: Initially 10 eligible subjects will be treated with Hu5F9-G4 (magrolimab) and dinutuximab at RP2D; if 0 responses (PR or CR) occur, enrollment will stop to this cohort. If 1 or more subjects respond, enrollment will continue to a total of 20 subjects with measurable osteosarcoma treated at the RP2D. If 3 or more evaluable subjects with measurable disease have a response, this combination in this cohort will be considered of sufficient interest to warrant additional study. The following Simon's optimal two stage design will be used for this cohort:

	Cumulative Number of Responses	Decision
Stage 1: Enter 10	0	Terminate this cohort: agent ineffective
patients	1 or more	Inconclusive result, continue cohort to enroll to stage 2
Stage 2: Enter	2 or less	Terminate this cohort: agent ineffective
additional 10 patients	3 or more	Terminate this cohort: agent effective

Measurable soft tissue disease will be evaluated using either CT or MRI, and lesions will be measured according to RECIST Version Date: 02/02/2024 Page 82

v1.1., and responses will be determined as either complete response (CR), partial response (PR), stable disease (SD) or progressive disease (PD). Response rates will be calculated for the osteosarcoma cohort whose best response is a CR or PR. Response is defined relative to baseline disease. This combination will not be considered to be of sufficient interest for further evaluation if the true response rate is 5% and of sufficient activity if the true response rate is 25%. If the combination has a true response rate of 5%, the rule described above will identify it of sufficient activity for further study with a probability of 0.07 (type1 error) and the trial will have an expected sample size of 14 with 60% probability of early termination. If the combination has a true response rate of 25%, the rule described above will identify it of sufficient activity for further study with probability 0.88 (power against the alternative hypothesis P = 0.25).

# **9.2.3** Expansion Cohort B4 Primary Endpoint

The primary objective for the expansion cohort B4 is to determine the safety and feasibility of administering Hu5F9-G4 (magrolimab) in combination with dinutuximab to patients that undergo recent resection of metastatic osteosarcoma within three weeks of surgery.

Ten (10) evaluable subjects will be treated with Hu5F9-G4 (magrolimab) and dinutuximab at RP2D. If 3 or more subjects out of the 10 subjects experience complications, the lower bound of the 95% Clopper-Pearson confidence interval on the proportion of complications will be higher than 5%. Thus, if 3 or more subjects out of the 10 subjects experienced complications, the use of Hu5F9-G4 (magrolimab) in combination with dinutuximab after surgery would be considered not feasible.

# 9.3 Sample Size/Accrual Rate

# **9.3.1** Proposed Sample Size

A minimum of 4 patients and a maximum of 82 patients will be enrolled on this trial.

# 9.3.2 Accrual Rate

The expected accrual is 2-3 patients per month (slower during dose escalation, more rapid during expansion cohorts). We estimate that accrual will be completed within about 36 months.

#### **9.3.3** Sample Size Justification

A minimum of 4 patients will be enrolled on this trial if two patients at Dose Level 1 have DLTs and 2 patients at Dose Level -1 have DLTs.

A maximum of 82 patients will be enrolled on this trial:

- Six patients/dose level at Dose Level 1 and Dose Level -1 = 12
- Three expansion cohorts (B1, B2 and B3) of 20 patients in each cohort
- Ten patients in cohort B4.

# 9.4 Demographics

This trial is open to all participants regardless of gender or ethnicity. Efforts will be made to extend the accrual to a representative population; however, in a Phase1 trial, which will accrue a limited number of patients, a balance must be struck between patient safety considerations and limitations on the number of individuals exposed to potentially toxic or ineffective treatments on the one hand and the need to explore gender, racial, and ethnic aspects of clinical research on the

other. If differences in outcome that correlate to gender, racial or ethnic identity are noted, accrual may be expanded, and/or additional studies may be performed to investigate those differences more fully.

#### PLANNED ENROLLMENT REPORT

	Ethnic Categor				
Racial Categories	Not Hispanic or	· Latino	Hispanic or I	Total	
	Female	Male	Female	Male	
American Indian/ Alaska Native	0	0	0	0	0
Asian	3	4	0	0	7
Native Hawaiian or Other Pacific Islander	1	2	0	0	3
Black or African American	5	6	0	0	11
White	15	22	7	9	53
More Than One Race	2	3	1	2	8
Total	26	37	8	11	82

PHS 398 / PHS 2590 (Rev. 08/12 Approved Through 8/31/2015)

OMB No. 0925-0001/0002

# 9.5 Analysis of Secondary Endpoints

**9.5.1** Determine the pharmacokinetics (PK) of Hu5F9-G4 (magrolimab) in children and young adults.

The endpoint for PK analysis is to assess the drug concentrations achieved during this first in child trial. Samples will be collected in the Safety Lead-In cohort and the first 3 patients on any expansion cohorts on the following schedule:

- Safety Lead-In: Day 1, Day 8, Day 15
- Cycle 1: Day 1, Day 8, Day 15
- Cycle 2, 3, 5, 7, 9, 11: Day 1
- End of Therapy

These samples will be a mandatory in the Safety Lead-In cohort and in the first three patients on any expansion cohorts (B1, B2, B3 and B4).

The PK Analysis Set will be used for summaries of PK concentration of magnolimab versus time. Serum concentrations will be listed and summarized for magnolimab using descriptive statistics by sampling timepoint and cohort. Graphical plots of individual serum concentration versus time and mean concentration versus time by cohort will be generated. The samples will be tested and analyzed by PPD.

## **9.5.2** Observe and record anti-tumor activity

Although the clinical benefit of this combination of drugs has not yet been established, the intent of offering this treatment is to provide a possible therapeutic benefit, and thus the patient will be carefully monitored for tumor response and symptom relief in addition to safety and tolerability.

All eligible patients will be considered evaluable for response if they receive any doses of the combination regimen. Antitumor activity will be evaluated in patients with osteosarcoma according to Section 12.1 and in patients with neuroblastoma according to Section 12.2.

**9.5.3** Evaluate the Event Free Survival (EFS) in two cohorts of osteosarcoma patients who are treated at the RP2D (measurable relapsed osteosarcoma and patients with pulmonary relapse undergoing resection) and compare to historical controls (Lagmay et al., 2016).

In this trial EFS is defined as the time from the first dose of Hu5F9-G4 (magrolimab) until the earliest of: death, local recurrence, new metastatic disease, progression of metastatic disease or secondary malignancy, or date of last contact. The historical control report of EFS for 96 patients with osteosarcoma and measurable disease was 12% at 4 months (95% CI, 6% to 19%). This study will compare the EFS of patients in the expansion cohort 3 (measurable osteosarcoma) to these historical controls.

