#### 3.1.3 Disease Status

Patients must have measurable or evaluable disease as follows:

- 3.1.3.1 Cohort B1: Confirmed neuroblastoma: measurable NBL/ganglioneuroblastoma (defined as those lesions that can be accurately measured in at least one dimension (longest diameter to be recorded) as ≥ 10 mm with cross sectional imaging (CT scan or MRI), or ≥ 10 mm with calipers by clinical exam). Chest x-ray cannot be used to determine eligibility. Lesions must be MIBG positive, PET avid (if patient has a history MIBG negative disease) or biopsy proven NBL/ganglioneuroblastoma.
- 3.1.3.2 **Cohort B2:** Evaluable NBL (MIBG and/or bone marrow disease only)
- 3.1.3.3 Cohort B3: Measurable osteosarcoma (defined as those lesions that can be accurately measured in at least one dimension (longest diameter to be recorded) as  $\geq 10$  mm ( $\geq 1$  cm) with cross sectional imaging (CT scan, MRI, or calipers by clinical exam). Chest x-ray cannot be used to determine eligibility.
- 3.1.3.4 **Cohort B4:** Patients with relapsed resectable pulmonary osteosarcoma who are scheduled for a surgical resection.

*Note:* Subjects will not have measurable disease due to recently resected pulmonary metastases. Investigational therapy must begin within three weeks of resection. Staged resections are permissible; investigational therapy will be administered in between resections. Patients should receive one cycle of investigational therapy in between resections but can receive additional cycles to accommodate the most appropriate surgical schedule as determined by the treating physicians. Every effort will be made to have at least half of this cohort (five of ten patients) be those requiring a staged resection.

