#### **6.5.2** Off Study Criteria

- a) Thirty days after the last dose of the investigational agent for patients who develop disease progression during combination therapy.
- b) The fifth anniversary of the date the patient was enrolled on this study, or until disease progression, for patients who complete the maximum number of cycles or who met off protocol therapy criteria in Section 6.5.1 other than disease progression.
- c) Withdrawal of consent for any required observations or data submission.
- d) The patient does not receive protocol treatment after study enrollment.
- e) Patient enrollment onto another COG study with therapeutic (anti-cancer) intent.
- f) Lost to follow-up.
- g) Death

The reason(s) for removal from protocol therapy, the reason(s) for the patient being off study, and the corresponding dates must be documented in the Case Report Form (CRF).

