## 6.6 **Duration of Follow-Up**

Patients who complete the maximum number of cycles or who met off-therapy criteria other than disease progression will be asked to participate in study follow-up and be evaluated at month 2 ( $\pm$  1 week), month 4 ( $\pm$  2 weeks), month 6 ( $\pm$  4 weeks), month 9 ( $\pm$  4 weeks), and month 12 ( $\pm$  2 months) and then yearly until year 5, or until disease progression.

Follow-up visits will be completed in-person unless the patient does not agree to continue in-person visits. In this case, telephone contact may be arranged to ensure the collection of as many safety and efficacy parameters as possible. The approach taken should be recorded in the CRF. A patient that agrees to modified follow-up is not considered to have withdrawn consent or to have withdrawn from the study.

Patients who develop disease progression during combination therapy will be followed for a minimum of 30 days after the last dose of study drug or study procedure, or until death, whichever occurs first. Patients removed from study for unacceptable adverse event(s) will be followed until resolution or stabilization of the adverse event and disease progression, whichever occurs later.

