# CHILDREN'S ONCOLOGY GROUP

#### PED-CITN-03

THIS PROTOCOL IS FOR RESEARCH PURPOSES ONLY, SEE PAGE 1 FOR USAGE POLICY

- Dinutuximab will be administered on Days 2-5 during the first week of every cycle as specified in Section 6.2. Administer antihistamines, antipyretics (i.e. acetaminophen and ibuprofen) and analgesia prior to each dinutuximab infusion as per Section 6.2.
-  Both height and weight will be recorded at screening. Only weight will be recorded at subsequent applicable visits.
- A complete physical examination as well as a cancer-specific physical exam will be performed at screening. Physical exams at subsequent applicable visits will be targeted based on the investigator's clinical observations and symptomatology. If a physical exam is performed within 3 days prior to a subsequent dosing day it does not need to be repeated on the dosing day provided there is no new status change.
- Vital signs = heart rate, respiratory rate, blood pressure, temperature, pulse oximetry. See Sections 6.2.1.4 for collection timepoints during and after infusion. Vital signs must also be collected at each non-dosing visit.
-  Karnofsky score of ≥50% is required for patients >16 years, and Lansky score of ≥50% is required for patients ≤16 years. Patients unable to walk due to paralysis, but who are using a wheelchair, will be considered ambulatory for the purpose of assessing the performance score. See APPENDIX A.
- Baseline disease evaluation will occur within 28 days of treatment initiation. During the treatment period Cycles 1 through 4, patients in Cohorts B1, B2 and B3 should be re-evaluated for response at the end of Cycles 2 and 4. After Cycle 4, disease evaluation will occur every 12 weeks (after every 4 cycles). Disease evaluations should occur within 7 days prior to dosing of the subsequent cycle. If treatment is delayed, disease evaluations will follow the originally scheduled calendar dates and should not be adjusted for the dose delay. The same method of assessment and technique should be used throughout the study. See Section 12 for disease parameters, methods of assessment, and response criteria. Cohort B4 refer to Section 12 for disease evaluation timepoints. For patients with neuroblastoma/ganglioneuroblastoma, bilateral bone marrow aspirates and trephine biopsies are required at all disease assessment time points (see Section 12.2) and Follow-up Visits for disease evaluation.

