# 12.1 Antitumor Effect – Osteosarcoma (Measurable disease)

Response and progression will be evaluated in this study using the new international criteria proposed by the revised Response Evaluation Criteria in Solid Tumors (RECIST) guideline (version 1.1) [Eur J Ca 45:228-247, 2009]. Changes in the largest diameter (unidimensional measurement) of the tumor lesions and the shortest diameter in the case of malignant lymph nodes are used in the RECIST criteria.

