#### **12.1.2** Disease Parameters

Measurable disease. Measurable lesions are defined as those that can be accurately measured in at least one dimension (longest diameter to be recorded) as  $\geq 10$  mm ( $\geq 1$  cm) with cross sectional imaging (CT scan or MRI), or calipers by clinical exam. All tumor measurements must be recorded in millimeters (or decimal fractions of centimeters).

*Note*: Tumor lesions that are situated in a previously irradiated area might be considered measurable.

Malignant lymph nodes. To be considered pathologically enlarged and measurable, a lymph node must be  $\geq$ 15 mm ( $\geq$ 1.5 cm) in short axis when assessed by CT scan (CT scan slice thickness recommended to be no greater than 5 mm [0.5 cm]). At baseline and in follow-up, only the short axis will be measured and followed.

Non-measurable disease. All other lesions (or sites of disease), including small lesions (longest diameter <10 mm [<1 cm] or pathological lymph nodes with  $\ge 10$  to <15 mm [ $\ge 1$  to <1.5 cm] short axis), are considered non-measurable disease. Bone lesions, leptomeningeal disease, ascites, pleural/pericardial effusions, lymphangitis cutis/pulmonitis, inflammatory breast disease, and abdominal masses (not followed by CT or MRI), are considered as non-measurable.

*Note*: Cystic lesions that meet the criteria for radiographically defined simple cysts should not be considered as malignant lesions (neither measurable nor non-measurable) since they are, by definition, simple cysts.

'Cystic lesions' thought to represent cystic metastases can be considered as measurable lesions, if they meet the definition of measurability described above. However, if non-cystic lesions are present in the same patient, these are preferred for selection as target lesions.

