## 12.1.4 Response Criteria

#### 12.1.4.1 Evaluation of Target Lesions

Complete Response (CR): Disappearance of all target lesions. Any pathological lymph nodes (whether target or non-target) must have reduction in short axis to <10 mm (<1 cm).

Partial Response (PR): At least a 30% decrease in the sum of the diameters of target lesions, taking as reference the baseline sum diameters.

Progressive Disease (PD): At least a 20% increase in the sum of the diameters of target lesions, taking as reference the smallest sum on study (this includes the baseline sum if that is the smallest on study). In addition to the relative increase of 20%, the sum must also demonstrate an absolute increase of at least 5 mm (0.5 cm). (Note: the appearance of one or more new lesions is also considered progressions).

Stable Disease (SD): Neither sufficient shrinkage to qualify for PR nor sufficient increase to qualify for PD, taking as reference the smallest sum diameters while on study.

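### The EFS definition in 9.5.3 omits progression of an existing local lesion and does not label last contact as censoring; objective 1.2.2 also extends a measurable-disease control to cohort B4

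*Combined protocol and SAP*

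**What the plan says.** Section 9.5.3 defines EFS for this trial as the time from the first dose of magrolimab "until the earliest of: death, local recurrence, new metastatic disease, progression of metastatic disease or secondary malignancy, or date of last contact". It does not refer to Section 12 and has no sentence on censoring. No other section supplies a censoring rule for EFS. The control value is 12% at 4 months (95% CI 6% to 19%), from 96 patients with osteosarcoma and measurable disease. The last sentence of 9.5.3 compares cohort 3 (B3) with it.

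Four other parts of the protocol bear on this:

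- **Who is in B3.** Section 3.1.3.3 requires "Measurable osteosarcoma (defined as those lesions that can be accurately measured in at least one dimension" at 10 mm or more. Local and metastatic sites both qualify.
- **What progression is.** Section 12.1 states that "Response and progression will be evaluated in this study using the new international criteria" of RECIST 1.1. Section 12.1.4.1 defines progressive disease as "At least a 20% increase in the sum of the diameters of target lesions, taking as reference the smallest sum on study", with an absolute increase of at least 5 mm. Section 12.1.4.2 adds unequivocal progression of existing non-target lesions. Neither rule depends on whether a lesion is local or metastatic.
- **Scans and follow-up.** The Arm B calendar in Section 11 says "patients in Cohorts B1, B2 and B3 should be re-evaluated for response at the end of Cycles 2 and 4". Under 6.5.2(a) a patient goes off study "Thirty days after the last dose of the investigational agent for patients who develop disease progression during combination therapy". Section 6.6 words it as "Patients who develop disease progression during combination therapy will be followed for a minimum of 30 days after the last dose of study drug".
- **Which cohorts are compared.** Objective 1.2.2 and the 9.5.3 heading name both osteosarcoma cohorts, B3 and B4. Section 3.1.3.4 notes that B4 patients have no measurable disease after resection.

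**The concern.** A B3 patient whose only progression is growth of a lesion at the local site has RECIST progression and stops protocol therapy. Read as written, 9.5.3 gives that patient no EFS event at that date. Local recurrence does not naturally describe a lesion that never went away, and the progression item is confined to metastatic disease. The patient's EFS time then runs to last contact.

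Last contact stands in the same list as the failures. If it censors, the local-only progressor leaves the risk set without an event and EFS is too high. If it is taken literally as an end point, patients who withdraw event-free count as failures.

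At stake is the only planned comparison of osteosarcoma efficacy with outside data, in a cohort of at most 20 patients. If the event definition is settled only at analysis, it can be settled with the data in view. For B4, the objective promises a comparison for which the text gives no fitting value.

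**Working it through.** **1. The plan's own figure.** Take p = 0.12, n = 96, a log-log interval, and no censoring before 4 months (assumed).

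- Standard error: sqrt(0.12 × 0.88 / 96) = 0.0332.
- On the log-log scale: 1.96 × 0.0332 / (0.12 × 2.120) = 0.2555.
- Limits: 0.12^exp(0.2555) = 0.065 and 0.12^exp(−0.2555) = 0.194.

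The stated 6% to 19% is reproduced, so the control value itself is not in question.

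**2. The two event lists side by side.**

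| Finding in a B3 patient | Progression under 12.1.4 | EFS event under 9.5.3 |
|---|---|---|
| New metastasis | yes | yes |
| Growth of an existing metastasis | yes | yes |
| Growth of an existing local target lesion | yes | not listed |
| Unequivocal growth of existing local non-target disease | yes | not listed |

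**3. When a local-only progressor leaves.** Priming is day 1 and Arm B Cycle 1 fills weeks 2 to 4, so Cycle k ends on day 7 + 21k.

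- Scans: day 49 (k = 2) and day 91 (k = 4).
- Last magrolimab dose before each scan: day 43 or day 85.
- Thirty days later: day 73 or day 115. Both fall before 4 months (about day 122).

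**4. Size if last contact censors.** Let q be the local-only share of progressions, assumed to be 5%, 10% or 20%. Take the true 4-month EFS as 12%, and assume local-only progressors have no other listed event before last contact.

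- Proportional-hazards model, 0.12^(1−q): 0.133, 0.148, 0.183.
- Two-scan model. S49 = 0.12^(49/91) = 0.319, and the apparent value is [1 − (1−q)(1 − S49)] × [1 − (1−q)(1 − 0.12/S49)]: 0.144, 0.170, 0.228.

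An apparent EFS of about 13-14%, 15-17% or 18-23% therefore stands in for a true 12%.

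**5. Last contact taken literally as an end point.**

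- Event-free withdrawal counted as a failure instead of censored: each lowers 4-month EFS by 0.12 / (n × S(t)), where S(t) is 1 before day 49, 0.319 from day 49 to 91, and 0.12 after day 91. At n = 20 this is 0.6, 1.9 or 5.0 points. The documents give no expected number of such withdrawals.
- Local-only progressor last seen on day 73 or 115: dated late, but still a failure by day 122, so the 4-month value does not move. If those found at day 91 stay in contact past day 122, it reads 0.12 + q × (0.319 − 0.12) = 0.130, 0.140 or 0.160.

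**6. B4.** Objective 1.2.2 and the 9.5.3 heading include B4. The last sentence of 9.5.3 names cohort 3 only, the one control value is for measurable disease, and B4 has none. These passages contradict each other.

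**The case against.** The best defence is that the intended event is not obscure. Section 12.1 sets RECIST 1.1 for progression throughout the study, and progression ends therapy and shortens follow-up, so few analysts would set aside a recorded progression. On this view 9.5.3 lacks only a cross-reference. The sentence also defines a time. Its clinical items close with secondary malignancy before last contact is added after a second conjunction, which reads as end of observation. Bone lesions are among those Section 12.1.2 treats as non-measurable ("Bone lesions, leptomeningeal disease, ascites, pleural/pericardial effusions"), which probably lowers the local-only share. No alpha, power, test or decision rule attaches to EFS.

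Most of this limits the weight of the point and is accepted. Last contact as censoring is the natural reading, and the literal one calls only for a clarifying sentence. But 9.5.3 presents its own self-contained definition, and where 9.5.2 sends the reader to Section 12, 9.5.3 does not. Non-measurable local disease can still progress under 12.1.4.2. Followed as written, the definition misses these patients.

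A reader might infer that the two wording faults bias EFS in opposite directions. That holds only for withdrawals under the literal reading; otherwise that reading leaves the 4-month value unchanged or raises it. A reader might also infer that no control for B4 exists. The documents quote one figure from one cited report and do not show whether it also covers resected patients.

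**Conclusion.** The point holds as a defect of definition that should be corrected. The wording gap, the missing censoring rule and the contradiction over B4 are plain from the text. Under the natural reading B3 EFS is biased upward. The sizes in steps 4 and 5 are illustrations: they rest on an assumed local-only share, an assumed true EFS of 12% and the model chosen.

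A larger bias is tempting to claim. If every local-only progressor counted as event-free at 4 months, the apparent value would be 0.12 + 0.88q, or 16.4%, 20.8% and 29.6% for the same shares. That needs contact past day 122 in all of them with no other listed event. Section 6.6 sets only a minimum, so longer contact is possible, but 6.5.2(a) takes these patients off study at 30 days and nothing schedules contact to 4 months.

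Nor do the documents show that the comparison with the control is biased in the treatment's favour. The control's event definition is not given; if it had the same gap, the two figures could be affected alike. EFS is secondary, and B3's go/no-go rule rests on response rate (9.2.2), which none of this touches.

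**What to change.** - **Event (9.5.3).** Define the event as the earliest of RECIST 1.1 progressive disease at any site (by reference to 12.1.4), recurrence, new metastatic disease, secondary malignancy, or death.
- **Censoring (9.5.3).** Remove last contact from the end points. State that patients without an event are censored, and name one rule: the date of last disease assessment or the date of last contact.
- **Control.** Look up the event definition in the cited report and note any difference from the trial's when the comparison is presented.
- **B4.** Reconcile 1.2.2 and the 9.5.3 heading with the last sentence of 9.5.3. Limit the measurable-disease comparison to B3. For B4, either supply a control value for resected disease, checking the cited report first, or report EFS descriptively.

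The cost is a few sentences and one look-up, with no extra scans or patients. The downside is that B3 EFS may come out slightly less favourable, and B4 may have no historical comparison.
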